8.4.3 Special Assays or Procedures

Blood sample collection

The following blood samples will be collected for mechanistic work at weeks 0 (baseline), 12, 36 and 60 using standard phlebotomy techniques:

- a). 1x 5 ml Z serumSep Clot Activator vacuette tube (gold top) for blood serum
- b). 1x remaining blood allowed for immunology (fresh PBMCs) and metabolic work (frozen PBMCs)

Sample transport, processing and storage for mechanistic work:

We aim to collect mechanistic samples for all patients recruited at St Thomas' Hospital at each of the four time points (0, 12, 36, and 60 weeks) for the immunology and metabolic work, and we will make use of our own fully established biobanking facilities at King's College London (KCL) to process and store samples.

Samples will be transported by courier, ensuring that they are fully processed by 4pm on the same day and within a maximum of 6 hours post venesection. The lab work will commence at the end of the trial and will be performed by full-time lab technicians in London.

Cutaneous tape strip collection:

Round adhesive tape discs (3.8 cm2, D-Squame; CuDerm, Dallas, Tex) will be attached to the skin of the forearm. Each tape will be pressed onto the volar aspect of the forearm for 10 seconds with standardized force by using a disc pressure applicator (CuDerm). The tape strip will be gently removed with tweezers and stored in a closed vial at -80°C until analysis. The first strip will be discarded because it might contain dirt and remnants of cosmetic

products; the second to sixth tape strips will be applied on the same skin spot. The tape strip samples will only be collected from patients recruited from St Thomas' Hospital.

Mechanistic studies:

Immunological parameters:

We will study whether significant changes are observed in the percentages of Tregs, in the percentages of pro/anti-inflammatory cytokine-expressing CD4+ T cells, or in the corresponding levels of these cytokines in serum following treatment, whether this is different in MTX vs CyA treated patients, and whether this correlates to response to treatment at 12 and 36 weeks and the risk of re-flares at 60 weeks.

• Systemic and local metabolic parameters:

We will examine whether the initial treatment response at 12 weeks to MTX (vs CyA) is already associated with differences in the systemic metabolic profiles (shift from pro-inflammatory glycolytic activation to an anti-inflammatory metabolic profile), and whether this is also seen at 36 and 60 weeks, explaining a more sustained disease remission following MTX (vs CyA) therapy. We will also study whether the observed systemic metabolic changes are associated with corresponding metabolic profiles and gene expression in the skin.

Urine (NAG)

Urine samples will be collected for mechanistic work at weeks 0, 2, 12. 36 and 60.

Sample transport, processing and storage

The following samples will require processing and storage at participating sites prior to transporting to the KCL Bio Bank/external laboratories (pg. 4-6):

- -Cystatin C
- -Creatinine
- -MTX metabolite levels
- -Ciclosporin trough levels
- -Urine (NAG)
- -Tape stripping
- -FLG

Processing of the samples can be carried out by a local research nurse or laboratory technician. Sample collection, processing and transport requirements are detailed in a sample manual, which will be provided to participating sites, and training in this will be provided at the site training visit.

8.5 Loss to Follow-up

If any of the trial participants are lost to follow up contact will initially be attempted through the PI or designated research staff at each centre. If the lead investigator at the trial centre is not the participant's usual clinician responsible for their specialist care then follow up will also be attempted through this latter clinician.

Where possible, information on the reason for loss to follow up will be recorded.

8.6 Trial Closure

The end of the trial is defined to be the date on which data for all participants is frozen and data entry privileges are withdrawn from the trial database. However, the trial may be closed prematurely by the Trial Steering Committee (TSC), on the recommendation of the

Independent Data and Safety Monitoring Committee (IDSMC). Should the trial be closed prematurely, all active participants (receiving treatment or in follow up) will be called in for a final follow up visit and assessments will be undertaken. Ongoing care will be at the discretion of the treating clinician.

9 STATISTICAL CONSIDERATIONS

9.1 Introduction

A separate and full statistical analysis plan (SAP) will be developed prior to the final analysis of the trial. The main features of these planned statistical analyses are included here in the main protocol.

9.2 Method of Randomisation

Participants will be randomised using a secure (24-hour) web-based randomisation programme controlled centrally by the CTRC. Randomisation lists will be generated in a 1:1 ratio using simple block randomisation with random variable block length (see section 6.4 for back-up randomisation method).

9.3 Outcome Measures

9.4 Co-Primary Endpoints

- 1. Change in atopic eczema severity between baseline and 12 weeks of treatment, using the o-SCORAD index.
- 2. Time to first significant flare after treatment cessation in the MTX vs CyA groups.

9.5 Secondary Endpoint(s)

- 1. Change in atopic eczema severity using the EASI, IGA, o-SCORAD and POEM between baseline and 12, 36, 48, and 60 weeks.
- 2. Number of flares in each study arm as well as the proportion of children who re-flared following treatment cessation.
- 3. Proportion of participants achieving 50% improvement in the o-SCORAD index at 12, 36, 48, and 60 weeks.
- 4. Proportion of participants who withdraw from treatment because of AEs.
- 5. Disease-specific patient and parental quality of life (QoL) measured with the CDLQI/IDQOL and DFI scores between baseline and 12, 36, 48 & 60 weeks.
- 6. Assess the cost-effectiveness of CyA vs MTX, based on utility measured using the CHU-9D.
- 7. Immuno-metabolic effects of MTX and CyA, especially in relation to markers of glycolytic activation and T cell cytokine signature, at baseline, during treatment and post treatment cessation.
- 8. Drug-related side effects of both MTX and CyA and their association with MTX polyglutamate and CyA trough levels.
- 9. The association between MTX polyglutamate and CyA trough levels and treatment response (reduction in disease severity).

10. The association between FLG carriage (yes/no) and treatment response.

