1 PROTOCOL SUMMARY

Study title:	Randomised controlled trial assessing the effectiveness, safety and cost-effectiveness of methotrexate (MTX) versus ciclosporin (CyA) in the treatment of severe atopic eczema in Children: The TRE atment of Severe A topic Eczema T rial (TREAT)
Protocol Short Title/Acronym:	TREAT Trial
Phase:	III
Co-Sponsor names:	King's College London and Guy's & St Thomas' NHS Foundation Trust
Chief Investigator:	[name]
Eudract number:	2015-002013-29
REC number:	15/EE/0328
Study design:	Randomised multicentre trial comparing methotrexate (MTX) and ciclosporin (CyA) in patients with severe paediatric atopic eczema. 102 participants will be randomised applying a ratio of 1:1.
Population:	Children age 2-16 years with severe atopic eczema (o-SCORAD≥30) and inadequately responding to potent topical treatment. Children should not have received UV light therapy within the past 6 months & should never have received any systemic immuno-suppressive therapy, except for oral corticosteroids for acute flares.
Centres and Distribution:	Secondary and tertiary paediatric dermatology centres.
Study Duration:	All participants will be treated for 36 weeks on either therapy, with another 24 weeks follow up post treatment cessation (total duration 60 weeks per participant).
Intervention:	 CyA: 4mg/kg/day (in divided doses); OR MTX: started at 0.1mg/kg/week (initial test dose) and then continued on 0.4mg/kg/week from week 1 (Max dose = 25mg/week)). Tablet or oral solution as standard, but MTX can be given subcutaneously if gastrointestinal side effects warrant this.
Primary Objective:	The study has two co-primary objectives. 1. To assess the change in atopic eczema severity between baseline & 12 weeks of treatment in the two treatment arms, and 2. To examine disease remission (time to first significant flare) after treatment cessation in the MTX vs CyA groups.
Secondary Objective/s:	-To examine atopic eczema severity using the Eczema Area & Severity Index (EASI), Investigator Global Assessment (IGA), objective SCORing Atopic Dermatitis (o-SCORAD) & Patient Orientated Eczema Measure

(POEM) scores between 0 and 12, 36, 48, 60 weeks and
using the o-SCORAD at 36, 48 and 60 weeks

-To compare the number of flares in each study arm as well as the proportion of children who re-flared following treatment cessation.

-To study the impact on quality of life: change in CDLQI/IDQOL & DFI scores between 0, 12, 36, 48 and 60 weeks

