8.2 Procedures for Assessing Efficacy

Efficacy of trial treatments will be assessed throughout the period of the study using objective measures.

The first co-primary outcome measure for the trial is change in atopic eczema severity between baseline and 12 weeks of treatment, using the objective SCORing Atopic Dermatitis (o-SCORAD) severity index, conducted by the blinded assessor (independent member of the research team) at baseline and at 12 weeks.

The second co-primary outcome is the time to the first significant flare after treatment cessation in the MTX vs CyA groups. The total number of flares will also be recorded in questionnaires. The time to the first significant flare is defined as the (earliest) time that a patient either re-started systemic treatment or returns to their baseline o-SCORAD (or worse), following cessation of trial treatment*.

The secondary outcome of change in atopic eczema severity using the o-SCORAD, EASI, IGA and Patient Oriented Eczema Measure (POEM) scores will be assessed between baseline and 12, 36, 48, 60 weeks.

* This refinement to the definition of the co-primary outcome was made, as it was felt that many patients may not ever return to their baseline (or worse) o-SCORAD following treatment cessation but still require systemic therapy because of the severity of their disease and/or the impact this has on their quality of life. The original wording of the definition did not fully reflect real world practice and treatment of a significant disease re-flare after systemic treatment cessation. The TMG consequently proposed the suggested refinement of the definition which was subsequently agreed by the independent oversight committees of the trial, the IDSMC and TSC. Those involved in the decision making were blind to all study results.

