9.6 Sample Size

For the first primary outcome (o-SCORAD), the change from baseline to 12 weeks will be calculated for each participant. The study aims to detect a difference of 8 o-SCORAD points, assuming a standard deviation (SD) of 10 (based on the only other paediatric RCT with systemic immunosuppressive medication in children (7), which saw a SD of 6.3 (MTX arm) vs 8.9 (CyA arm) at 12 weeks) a sample size of 41 per group, increasing to 49 per group to allow for an estimated 18% loss to follow up, will be required to provide 90% power using a t-test with a 0.025 two-sided significance level. Our assumption of 8 Units in the o-SCORAD index representing the minimal clinically important difference between treatments is based on calculations from three other RCTs with immuno-suppressive medication in children and adults with severe atopic eczema (33).

The co-primary outcome of this trial is time to first significant flare after treatment cessation (return to baseline o-SCORAD (or worse) or re-starting systemic treatment), as this may be an important factor influencing potential change in prescribing behaviour. The number of patients on CyA burst treatment who went into remission after the first three months of treatment in the study by Harper et al was three out of 21, indicating that 86% of patients reflared. Assuming a similar flare risk in our CyA group, a sample size of 43 in each group (51 in each group with estimated loss to follow up of 18%) will have 80% power to detect a reduction in re-flare of 30% (from 86% to 56%) using a two-sided test with a 0.025 significance level.

Randomising a total of 102 participants, 51 into each of the study arms, satisfies both sample size calculations.

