The analysis of change in o-SCORAD from baseline to 12 weeks will use the method of analysis of covariance and the covariates that will be used in the model will be treatment group and the baseline measurement

Analysis of time to first significant flare after treatment cessation will be summarised by Kaplan-Meier curves for each treatment group and compared overall using the log rank test and survival regression methods. The time to first significant flare after treatment cessation will be measured from randomisation.

For the secondary outcomes, continuous data will be reported as difference in means and will be analysed using ANCOVA where appropriate and binary data will be reported in terms of relative risk with appropriate 95% confidence intervals.

Missing data will be monitored and strategies developed to minimise its occurrence. Missing data will be handled by considering the robustness of the complete case analysis to sensitivity analyses using various imputation assumptions; however these will be informed by data collected on the reasons for missing data.

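### Week-48 and week-60 severity and 50%-improvement endpoints take no account of restarted systemic treatment, so as-observed results cannot be read as disease control after cessation

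*Protocol*

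**What the plan says.** The protocol summary (section 1) sets the timeline: "All participants will be treated for 36 weeks on either therapy, with another 24 weeks follow up post treatment cessation". After week 36, the schedule in section 8.1 has blinded severity assessments at weeks 48 and 60 only.

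Section 9.5 defines two sets of score endpoints that run into this period: "Change in atopic eczema severity using the EASI, IGA, o-SCORAD and POEM between baseline and 12, 36, 48, and 60 weeks" and "Proportion of participants achieving 50% improvement in the o-SCORAD index at 12, 36, 48, and 60 weeks". Neither mentions treatment restarted after cessation. Section 9.7 assigns the method ("For the secondary outcomes, continuous data will be reported as difference in means and will be analysed using ANCOVA where appropriate", with relative risks for binary outcomes) and adds no such condition.

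The second co-primary treats restart differently. Section 8.2 defines time to first significant flare as "the (earliest) time that a patient either re-started systemic treatment or returns to their baseline o-SCORAD (or worse), following cessation of trial treatment". Its footnote explains that restart was added because many children might never return to their baseline score and yet still need systemic therapy.

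Two other places bear on how the late results will be read. Section 2.4.2 calls disease control over the six-month follow-up a secondary outcome. Section 8.4.3 looks to metabolic profiles at weeks 36 and 60 as "explaining a more sustained disease remission following MTX (vs CyA) therapy".

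**The concern.** Take a child who relapses at week 40, restarts systemic treatment and is 60% better than baseline at week 60. That child is a flare in the second co-primary and an achiever in the 50%-improvement endpoint. Both records are correct, but they answer different questions, and the protocol does not say which one the late scores answer.

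The arm with more relapses will tend to have more children back on a systemic drug at weeks 48 and 60, which improves that arm's scores. If the late results are taken as disease control off treatment, as section 2.4.2 invites, a small or absent difference could be reported as equal durability when the arms differ in relapse. The week-60 mechanistic comparison has a similar weakness: a difference between arms could reflect who is currently on a drug and not lasting remission.

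**Working it through.** **The plan's own figure.** Section 9.6 states 43 per group for flare risks of 86% and 56%, two-sided 0.025, 80% power. With the pooled normal formula, n = [2.241 × √(2 × 0.71 × 0.29) + 0.842 × √(0.86 × 0.14 + 0.56 × 0.44)]² / 0.30² ≈ 42.2, so 43. The figure reproduces, and the two flare risks are used below.

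**Inputs**
- Flare risk f: 0.86 (ciclosporin) and 0.56 (methotrexate), from section 9.6. They are planning values for the follow-up as a whole, so they are applied to week 60. Week 48 works the same way with whatever flare risks hold by then.
- r0, probability of 50% improvement if unflared: assumed.
- q, share of flared children who have restarted by the visit: assumed.
- r1, probability of 50% improvement after restart: assumed.
- Flared and not restarted: assumed to have no responders. All assumed rates are taken as equal in the two arms.

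**Formulas**
- As observed: P = (1 − f) × r0 + f × q × r1. Methotrexate minus ciclosporin = 0.30 × (r0 − q × r1).
- Restart counted as not achieved: P = (1 − f) × r0. Difference = 0.30 × r0.

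The as-observed difference is therefore smaller whenever q × r1 is above zero. It vanishes when q × r1 = r0 and reverses when q × r1 exceeds r0.

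**Worked case** (r0 = 0.7, q = 0.8, r1 = 0.6)
- As observed, ciclosporin: 0.14 × 0.7 + 0.86 × 0.48 = 0.098 + 0.413 = 51%.
- As observed, methotrexate: 0.44 × 0.7 + 0.56 × 0.48 = 0.308 + 0.269 = 58%.
- The difference is 6.6 points.
- Restart as not achieved: 9.8% against 30.8%, a difference of 21 points.

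**Ranges**

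| Assumptions | As observed | Restart = not achieved |
|---|---|---|
| r0 = 0.7, q 0.5–1.0, r1 0.5–0.7 | 0 to +13.5 points | +21 points |
| r0 0.6–0.9, q 0.5–1.0, r1 0.4–0.9 | −9 to +21 points | +18 to +27 points |

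The ends of the wider as-observed range are 0.30 × (0.6 − 1.0 × 0.9) = −0.09 and 0.30 × (0.9 − 0.5 × 0.4) = +0.21.

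**Power, as an illustration** (43 per group, two-sided 0.05, r0 = r1 = 0.8). With restart as not achieved, response is 11.2% against 35.2% and power is 76%. As observed, power is 20% at q = 0.5 (45.6% against 57.6%) and 8% at q = 0.75 (62.8% against 68.8%). At q = 1 there is no difference left to detect.

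The same mechanism acts on mean EASI, IGA, o-SCORAD and POEM at these weeks. It is not quantified here, because the protocol gives no score distributions after cessation.

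**The case against.** The strongest reply is that nothing is misdefined. Scores for all participants whatever they later take are a recognised treatment-policy estimate. That fits section 6.5, which keeps children in follow-up after trial treatment stops, and section 8.4.2, where change in o-SCORAD and POEM feeds the within-trial cost-effectiveness analysis. This stands, and the as-observed analysis should stay.

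A reader might infer that the protocol treats restarted children as if they were off treatment. It does not; it sets no condition either way. Where section 9.5 means after cessation it says so, in endpoints 2 and 7, and the score endpoints carry no such label. A separate statistical analysis plan is announced in section 9.1, is not shown here, and may deal with restarts.

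A reader might also infer that the trial loses the remission difference. It does not. The second co-primary and the re-flare proportion in secondary endpoint 2 measure relapse, with restart counted as an event.

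The threefold ratio in the worked case (31% against 10%) should not be taken as information lost. It is 44/14, the assumed ratio of unflared children, because r0 cancels. Only the two flare risks come from the protocol; every other rate is assumed.

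On the mechanistic work, section 8.4.3 already plans to relate immunological changes to the risk of re-flares, and section 8.1.1 limits these samples to one hospital, so descriptive presentation is all that can be asked.

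What remains is that section 2.4.2 invites the off-treatment reading, and the footnote in section 8.2 recognises that scores alone miss children who still need systemic therapy.

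**Conclusion.** The point holds as one of interpretation, for weeks 48 and 60 only. The late severity and 50%-improvement endpoints are unconditional on restarted treatment, while the second co-primary counts restart as failure. If one arm relapses more and retreatment works, the as-observed responder difference understates the difference in disease control without retreatment, and it can vanish or change sign. Given the protocol's 30-point difference in flare risk and rates equal across arms, the shrinkage is 0.30 × q × r1. That is 14.4 points in the worked case, from 21 to 6.6. The direction of the shift follows from the flare assumption and from retreatment having some effect; its size rests on q and r1, and whether a difference is left also on r0, none of which the documents give. This is not an error in the as-observed analysis, and it does not touch either co-primary. It is an inexpensive improvement that would stop a diluted null from being reported as equal durability.

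**What to change.** 1. In sections 9.5 and 9.7, state that the as-observed week-48 and week-60 results are regardless of restarted systemic treatment and are not to be read as off-treatment disease control.
2. Add a pre-specified analysis of 50% improvement at weeks 48 and 60 in which a restart of systemic treatment after cessation counts as not achieved. Use the same restart definition as the second co-primary, and report it beside the as-observed result.
3. Present the week-60 mechanistic results by restart status, descriptively.
4. Leave the continuous scores as observed, with the statement in item 1. Do not substitute the last score at or before restart. Between visits, severity is recorded only if an unscheduled visit occurs, so for a restart before week 48 that score may be the week-36 one, taken at the end of treatment. It would credit a relapsed child with an on-drug value.

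The cost is some wording and one extra analysis to report. Restart dates are already needed for the second co-primary, and section 7.7 has concomitant medication recorded to week 60, so no new data are required. If the statistical analysis plan already contains such an analysis, only the protocol wording needs to be brought into line.
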